	The outcome will be determined by the modified pouchitis disease activity index (mPDAI) and the need for antibiotic therapy to control symptoms. The mPDAI is a composite index consisting of 2 disease variables (clinical criteria of pouchitis: number of bowel movements, blood in stool, urgency and fever with a maximum score of 6 and endoscopy criteria of pouch inflammation with a maximum score of 6. The maximum combined score is 12).	
	 Complete remission is defined as a mPDAI score = 0 and no need for antibiotics. Clinical remission is defined as a clinical mPDAI score ≤ 4 and no need for antibiotics. Symptomatic improvement is defined as a decrease from baseline in the mPDAI clinical subscore of 2 points and no need for antibiotics. Symptomatic worsening of the disease is defined by an increase in the mPDAI clinical subscore of 2 points or the need for antibiotics. 	
	The severity of the pouch inflammation will be evaluated by two pouchoscopies (week 0 and week 4). Endoscopic improvement is defined as a decrease from baseline in the mPDAI endoscopic subscore of 2 points.	
Primary variables	Safety and tolerability of endoscopically and orally applied FMT	
Secondary variables:	 Clinical remission (mPDAI score ≤4 points) and no need for antibiotic therapy at week 4. Clinical remission (clinical mPDAI score ≤ 4) and no need for antibiotics at week 8*. Clinical remission (clinical mPDAI score ≤ 4) and no need for antibiotics at week 16*. Endoscopic improvement of active pouchitis (decrease from baseline in mPDAI endoscopic subscore ≥ 2 points) at week 4. 	

	 Response: Symptomatic improvement of active pouchitis (decrease from baseline in mPDAI clinical subscore ≥ 2 points) and no need for antibiotic therapy at week 4. Response: Symptomatic improvement of active pouchitis (decrease from baseline in mPDAI clinical subscore ≥ 2 points) and no need for antibiotic therapy at week 8*. Response: Symptomatic improvement of active pouchitis (decrease from baseline in mPDAI clinical subscore ≥ 2 points) and no need for antibiotic therapy at week 8*. Response: Symptomatic improvement of active pouchitis (decrease from baseline in mPDAI clinical subscore ≥ 2 points) and no need for antibiotic therapy at week 16*. 	
	*Only patients who do not continue in open label extension	
	• Exploratory analyses (OL=Open label):	
	 Endoscopic improvement of active pouchitis (decrease from baseline in mPDAI endoscopic subscore ≥ 2 points) at in open label extension week 8. 	

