 - Active pouchitis, defined as a mPDAI \geq 5 and a history of \geq 4 antibiotic therapies for pouchitis in the last 12 months

or

Need for ongoing antibiotic therapy (> 4 weeks) to maintain clinical remission and a history of at least 2 attempts in the last 24 months to stop antibiotic therapy resulting in pouchitis episodes. Concomitant oral 5 ASA or local therapies containing 5-ASA (enemas, suppositories) or steroid enemas are permitted but not required but have to be stable for 4 (oral) or 2 weeks (topical) before inclusion in the study.

- Exclusion criteria
- Treatment with biologics (e.g. infliximab, adalimumab, golimumab, vedolizumab)
- Treatment with immunomodulators (azathioprine, 6-MP, methotrexate), steroids or any investigational drugs
- Use of cholestyramine
- Crohn's disease of the pouch
- Known cytomegalovirus infection of the pouch
- Clostridium difficile infection
- Isolated moderate or severe cuffitis
- Clinical significant strictures of the pouch inlet or outlet
- Concurrent intestinal obstruction
- History of familial adenomatous polyposis
- History of uncontrolled lactose intolerance
- History of confirmed (serological test and/or histology) celiac disease
- Pregnancy, breast feeding, or planning to become pregnant during the trial
- Non steroidal inflammatory medications (NSAIDs) as long-term treatment, defined as use for at least 4 days a week each month
- Dysphagia (oropharyngeal, esophageal, functional, neuromuscular)
- History of recurrent aspiration episodes
- Proven gastroparesis
- Allergy to the following generally regarded as safe ingredients (GRAS): glycerol, acid resistant HPMC, gellan gum, cocoa butter, titanium dioxide
- Adverse event attributable to previous FMT
- Allergy/intolerance to pump inhibitor therapy
- Any condition for which the investigator thinks the FMT treatment may pose a health risk (e.g. severely immunocompromised)
- Participation in another clinical trial within the last 30 days, simultaneous participation in another clinical trial, or previous participation in this trial
- During the trial period until one week after the trial end: Non-use of appropriate contraceptives in females of childbearing potential (e.g. condoms, intrauterine device {IUD}, hormonal contraception, or other means considered adequate by the responsible investigator) or in males with a child-fathering potential (condoms, or other means considered adequate by the responsible investigator during treatment

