7. OVERVIEW OF TRIAL SEQUENCE

See also study flow chart in appendix as well as study visit charts in appendix.

The trial will begin with the **screening visit (days -14 to 0).** The investigator will ask patients who are interested in participating in the study after a careful explanation, to sign an informed consent form prior to study specific examinations. The study patient will receive a copy of the consent form, which outlines the sequence of events in brief and summarizes the advantages and disadvantages of participation in the study.

After the patient has given his/her written consent, the screening examination will be performed to evaluate whether the patient is probably eligible for the study.

At the screening visit, a complete history will be taken including concomitant medication and demographic data will be collected. A physical examination will be performed and vital signs will be documented. Blood samples (max. 20 ml) will be taken from the study patient (all study patients: hematology, serum chemistry, creatinine, female study patients: urine samples for pregnancy test). Also the study patient will be provided with a stool collection kit to provide a stool sample, which should be collected at this visit or before the week 0 visit. This stool kit will also contain a sample kit for C. difficile toxin. The study patient will also be provided with a diary, which he/she will be asked to complete the diary every day in the evening during the trial. It will be also evaluated if the patient is able to swallow the oral FMT test capsule.

At least 10 days before the planned endoscopic FMT at week 0 all patients will be started on antibiotic therapy as standard of care for treatment of pouchitis. Patients on continuous antibiotic therapy will continue their regimen. Since all patients must fulfil the criteria for antibiotic pouchitis, the antibiotic with the best efficacy to treat the pouchitis episodes in the past will be used. In patients on chronic antibiotic therapy to prevent pouchitis recurrence the antibiotic regimen will be continued. 24 hours before the planned FMT the antibiotic will be discontinued.

Placebo-controlled trial period

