At week 0 visit the study patient will have a physical exam and a urine pregnancy test. The patient's AE and symptom diary should be reviewed and the clinically modified PDAI calculated. The patient's concomitant medications will be reviewed. If the study patient fulfils all inclusion criteria and does not have an exclusion criterion the study patient will be randomized to either the placebo or the FMT group and a unique study ID number will be assigned, which will appear on all medication packs.

The study patient then undergoes a pouchoscopy for evaluation of the pouch inflammation and to rule out complications in the pouch structure (e.g. strictures, isolated cuffitis, which would lead to exclusion of the trial). If all inclusion criteria are met during an endoscopically guided placebo or real FMT will be performed. Additionally, the study patient will be started on omeprazole 20 mg (1 tablet/daily) as

long as he/she undergoes oral FMT or placebo therapy. The study patient will receive 2 diaries, which need to be filled out on a daily basis, the stool diary and the adverse event diary. The stool diary should be daily completed either until Visit 8 or if the patient participates in the open label extension until visit 12OL. The adverse event diary has to be daily completed until visit 6 or visit 10OL.

At visits 2 and 4 (phone visits) the coordinator will ask the study patient if adverse events occurred and will review the adverse event diary with the study patient. The coordinator will also evaluate the clinical components of the mPDAI of the last 3 days before the phone call (stool frequency, rectal bleeding, fecal urgency/ abdominal cramping, fever) as well as the concomitant medications.

Visit 3 (site visit) the coordinator will review the adverse event diary with the study patient, and will assess the mPDAI and concomitant medication. The patient will also bring a stool sample for the stool bank, which was collected earliest on day 1 after the end of the oral or placebo FMT period.

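### Week-0 randomisation comes before the pouchoscopy that checks two exclusion criteria, so patients who are never treated can be randomised and, read literally, count as non-responders

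*Combined protocol and SAP*

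**What the plan says.** Section 7 (Placebo-controlled trial period) sets out week 0 in this order.

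1. After physical examination, pregnancy test, diary review, clinical mPDAI and medication review: "If the study patient fulfils all inclusion criteria and does not have an exclusion criterion the study patient will be randomized". A study ID is assigned at this point.
2. Next: "The study patient then undergoes a pouchoscopy for evaluation of the pouch inflammation and to rule out complications in the pouch structure". The examples given are "strictures, isolated cuffitis, which would lead to exclusion of the trial".
3. Treatment then depends on a second eligibility check: "If all inclusion criteria are met during an endoscopically guided placebo or real FMT will be performed".

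Both endoscopic findings are formal exclusion criteria in Section 6: "Clinical significant strictures of the pouch inlet or outlet" and "Isolated moderate or severe cuffitis".

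No earlier endoscopy is scheduled. According to Section 7, at screening "the screening examination will be performed to evaluate whether the patient is probably eligible for the study". The screening-visit list in Section 8 contains no pouchoscopy, the visit chart in Section 21 places it at Visit 1, and the Protocol Summary states: "The severity of the pouch inflammation will be evaluated by two pouchoscopies (week 0 and week 4". Only the pouchoscopy heading in Section 11 names screening.

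Section 8 (Visit 5) lists ineligibility discovered after recruitment as a reason for premature withdrawal. Section 20 (Clinical analyses) counts every subject with missing endpoint data as a non-responder under intention to treat and computes its measures on all 20 subjects. The intention-to-treat set is not defined, and there is no replacement rule.

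**The concern.** The plan requires that no exclusion criterion be present before randomisation, yet it schedules the examination for two of those criteria after randomisation. A patient who fails at that examination has an allocation and a study ID but receives neither transplant nor placebo.

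The analysis of that patient is then open. Kept as a non-responder, the patient dilutes the remission rate, mainly if allocated to FMT, because the assumed placebo rate is already only 10%. Dropped, the patient makes the analysis something other than intention to treat, and the 1:1 balance can be lost. This matters because the pilot's stated purpose is to supply effect sizes for a larger trial. With 10 patients per arm, one patient is a tenth of an arm.

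**Working it through.** **Inputs** (Section 20, Sample size calculation): 20 patients, 1:1, so 10 per arm; remission 77.5% on FMT and 10% on placebo; two-sided Fisher exact test, alpha 0.05; stated power 80%. The documents give no rate of exclusion at pouchoscopy, so results are given per excluded patient.

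**Reproducing the plan's figure.** Power is the sum, over all pairs (a, b) with Fisher p ≤ 0.05, of Bin(a; 10, 0.775) × Bin(b; 10, 0.10). This gives 0.802, which matches the stated 80%.

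**Excluded patients kept as non-responders.** With k excluded patients in an arm, remissions in that arm follow Bin(10 − k, p) while the denominator stays at 10. The expected rate is p × (10 − k)/10.

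- FMT, one excluded: 0.775 × 9/10 = 69.75%. FMT, two excluded: 0.775 × 8/10 = 62%.
- Placebo, one excluded: 0.10 × 9/10 = 9%. Placebo, two excluded: 0.10 × 8/10 = 8%.

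| Excluded (FMT, placebo) | Expected rates | Difference, points | Power |
|---|---|---|---|
| 0, 0 | 77.5% v 10% | 67.5 | 80.2% |
| 1, 0 | 69.75% v 10% | 59.75 | 67.4% |
| 0, 1 | 77.5% v 9% | 68.5 | 82.3% |
| 2, 0 | 62% v 10% | 52.0 | 51.3% |
| 1, 1 | 69.75% v 9% | 60.75 | 70.2% |
| 0, 2 | 77.5% v 8% | 69.5 | 84.3% |

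Averaged over which arm the patient falls in:

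- One excluded: difference (59.75 + 68.5)/2 = 64.1 points; power (67.4 + 82.3)/2, or 74.8%.
- Two excluded: the weights for two patients drawn from 20 are 45/190, 100/190 and 45/190. Power is (45 × 51.3 + 100 × 70.2 + 45 × 84.3)/190 = 69.1%.

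**Excluded patients dropped.** The denominators shrink and the rates stay at 77.5% and 10%.

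| Analysed (FMT v placebo) | Power |
|---|---|
| 9 v 10 | 83.9% |
| 10 v 9 | 82.3% |
| 9 v 9 | 79.5% |
| 8 v 10 | 80.8% |
| 10 v 8 | 79.9% |

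**Carry-over to the next trial.** Smallest n per arm with exact power of at least 80%:

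- 77.5% v 10%: 10
- 69.75% v 10% (one FMT-arm exclusion): 12
- 62% v 10% (two FMT-arm exclusions): 16
- 77.5% v 9% (one placebo-arm exclusion): 9

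**The case against.** The strongest reply is that non-responder scoring is only one reading. A patient excluded from the trial before any treatment may not be meant as one of the 20 analysed subjects, and the missing-data rule does not mention such patients. On that reading the harm is small: power stays between 79.5% and 83.9%, and a finding about pouch structure, made before treatment in a procedure described as blinded, costs mainly precision. This stands, and it limits the weight of the point. It does not remove it, because the plan does not say which reading applies.

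The order may also be a drafting slip, since the text allows randomisation only when no exclusion criterion is present. But that condition contradicts the sequence in the same section and does not resolve it. The Visit 1 list cannot settle the order either way, because the visit lists are grouped by topic. Likewise, the Section 11 heading may mean the week-0 procedure, since the screening window runs to day 0; it should still be reconciled with the chart.

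Three further points stand. No exclusion rate is given, history and physical examination at screening may catch some of these patients, and there may be none at all. Power is a secondary yardstick in a pilot with safety as primary endpoint: with 8 of 10 remissions the exact 95% interval is about 44% to 97%, far wider than a dilution of 7.75 points. The change from 10 to 9 per arm after a placebo-arm exclusion is mostly discreteness of the exact test, since 9 per arm already gives 79.5% at the original rates. Finally, if the larger trial kept the same order, the diluted rate would be the right planning input.

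**Conclusion.** The concern holds. As written, randomisation precedes the only endoscopic check of two exclusion criteria, and the plan does not say how a patient who fails that check is analysed or whether the patient is replaced.

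The size depends on the reading. Under literal non-responder scoring, one excluded patient costs on average about 5 points of power (80.2% to 74.8%) and about 3 points of the expected difference (67.5 to 64.1). The worst single case, in the FMT arm, costs about 13 points of power and 7.75 points of difference. If such patients are dropped, the cost is mainly precision and possible imbalance. All figures assume 77.5% and 10% among treated patients and an assumed one or two exclusions.

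This should be corrected but does not invalidate the trial: efficacy is secondary, the study is a proof of concept, and ineligible patients are not treated.

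**What to change.** In Sections 7 and 8, state that allocation is assigned and capsules are dispensed only after the diagnostic part of the week-0 pouchoscopy has confirmed eligibility, immediately before instillation. Record patients found ineligible at that look as screen failures who were not randomised. Reconcile the pouchoscopy heading in Section 11 with the visit chart.

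In Section 20, define the intention-to-treat set as all randomised patients. State how a patient found ineligible after randomisation for any other reason is analysed, and whether that patient is replaced.

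The cost is a re-ordering within one visit and two sentences in Section 20, with no extra procedure. Allocation and product preparation would have to wait for the endoscopic look, which may lengthen the visit. The documents do not describe how allocation is released or the product prepared, so the length of that delay cannot be judged from them.
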